11. STATISTICAL CONSIDERATIONS

This is a multicenter, open-label randomized phase IIa trial study to assess the effect and safety of Neoral (CSA) for treatment of COVID-19 (+) non-ICU hospital inpatients.

11.1 Primary Endpoint and Analytic Plan

The primary endpoint is the clinical outcome based on the World Health Organization (WHO) COVID Ordinal Clinical Improvement Scale (Table 2) on day 14. Wilcoxon rank sum test will be used to compare the ordinal scale between groups on day 14.

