2. BACKGROUND

2.1 Study Disease(s)

Severe acute respiratory syndrome coronavirus-2 (SARS-CoV-2) is a novel coronavirus that causes coronavirus disease 2019 (COVID-19). Since initial detection of the virus, more than 10 million cases of COVID-19 have been confirmed worldwide, and COVID-19 is responsible for more than 505,500 deaths. The United States has seen over 2.5 million cases of COVID-19

and 126,000 deaths from this disease (as of June, 30, 2020, source: Johns Hopkins University). SARS-CoV-2 is efficiently transmitted from person-to-person and the World Health Organization (WHO) has declared coronavirus disease 2019 (COVID-19) to be a pandemic. COVID-19 primarily spreads through the respiratory tract, by droplets, respiratory secretions, and direct contact. Current data suggest an incubation period of 1–14 days, in most cases 3–7 days. The virus is highly transmissible in humans and causes severe problems especially in the elderly and people with underlying chronic diseases. COVID-19 patients typically present with specific, similar symptoms, such as fever, malaise, and cough. Most adults or children infected with SARS-CoV-2 have presented with mild flu-like symptoms, but a few patients are in critical condition and rapidly develop acute respiratory distress syndrome (ARDS), respiratory failure, multiple organ failure, and death. The case fatality rate increases with the severity of illness and can reach up to 49% in critically ill patients (Wu).

Unfortunately, specific and effective therapies for COVID-19 are highly limited. Recent evidence suggest that administration of the anti-viral agent, Remdesivir, to hospital inpatients with COVID-19 decreases time to recovery from 15 to 11 days and decreases mortality at 14 days from 11.9% to 7.1% (Beigel). A preliminary, unpublished analysis from a large, multicenter, randomized, open-label trial for hospitalized patients in the United Kingdom showed that patients who were randomized to receive dexamethasone had a reduced rate of mortality compared to those who received standard of care. This benefit was observed in patients with severe COVID-19 and was greatest in those who required mechanical ventilation at enrollment (RECOVERY Trial). These 2 agents are considered in the standard of care (**SOC**) for treating patients with COVID-19. However, additional therapies with larger effect sizes and that are administered at earlier stages to prevent progression to severe COVID-19 are critically needed.

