2.2 Rationale

Severe COVID-19. Initial reports from cases identified between February 12 to March 16 in the United States (U.S.) show rates of hospitalization for COVID-19 to be 21–31%, intensive care unit (ICU) admissions to be 5–12%, and fatality to be 2%–3% [CDC COVID-19 Response Team 2020]. High-risk groups for severe COVID-19 have been identified as the elderly population and

those with underlying comorbidities such as cardiovascular disease, liver disease, pulmonary disease, renal disease, and diabetes mellitus [Xu 2020; Huang 2020].

Severe COVID-19 results from a dysregulated hyperimmune state. Severe symptoms of COVID-19 are associated with a hyperimmune response referred to as a cytokine storm. In one study, all 41 patients with COVID-19 admitted to the hospital demonstrated elevated plasma levels of cytokines and chemokines compared with healthy volunteers that included IL-1, -1R, -7, -8, -9, -10, and basic FGF2, GCSF, GMCSF, IFN- γ , IP10, MCP1, M1P1A, MIP1B, PDGF, TNF- α , and VEGF. Patients admitted to the ICU had higher levels of IL-2, IL-7, IL-10, GCSF, IP10, MCP1, MIP1A, and TNF- α than patients who did not require ICU admission [Huang 2020]. Emerging data has shown that early rapid SARS-CoV-2 replication causes massive epithelial and endothelial cell death that initiates a cytokine storm and vascular leakage, causes pyroptosis in macrophages and lymphocytes, and results in exhaustion of T cells and NK cells [Yang 2020][Chen2020][Zheng 2020].

COVID-19 similarities to hemophagocytic lymphohistiocytosis (HLH). HLH is an under-recognized, hyperinflammatory syndrome characterized by a fulminant and fatal cytokine storm and multi-organ failure. In adults, HLH is most commonly triggered by viral infections and occurs in 3.7% to 4.3% cases of sepsis. Cardinal features include unremitting fever, cytopenias, and hyperferritinemia. Pulmonary involvement (including ARDS) occurs in ~50% of patients. Each of these clinical features and a highly overlapping cytokine profile is seen in severe COVID-19. This demonstrates that the clinical presentation and pathologic mechanisms of severe COVID-19 is similar to, or is HLH.

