4.3 Randomization

Patients will be randomized in a 2:1 ratio to receive either CSA or placebo (no CSA). Randomization will be open-label, using the permuted block method and will be stratified by age (<60 or >60 years), WHO severity (4 vs. 5), presence or absence of comorbidities (at least one of the following – hypertension, coronary artery disease, congestive heart failure, or diabetes). Randomization will be performed centrally at the Baylor College of Medicine by the Project Manager.

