11.2 Sample Size /Justification

We expect to see higher grades of WHO COVID ordinal clinical scale in control group compared to the CSA treatment group, and propose to use a 1 to 2 randomization in favor of CSA group.

The total sample size of 75 evaluable participants will provide 81% power to reject the null hypothesis that the grade in control group is less than or equal to the CSA group with a 10% one-sided significance level when the true effect size, as measured by the probability that

Control grade is greater than CSA grade, is 0.65 or greater. Sample size and/or power for the various scenarios were calculated using nQuery 8 (StatSols Version 8.5.2.0).

The following provides the rationale for the alternate hypothesis effect size. We have assumed that all participants will be starting in category 4. Based on review of hospital data, about one third of such patients end-up in the ICU and about half of those patients will die. Of the two thirds that do not go to the ICU, most will be discharged in 2 weeks or less. We have therefore hypothesized that at 2 weeks following enrollment, the control group will be distributed as shown in the table 3.

We have hypothesized several scenarios to estimate the sample size needed to detect a CSA effect with reasonable power. We expect the effect of CSA will be to reduce ICU admissions, or to shorten time in the ICU and reduce deaths, so that the fraction in categories 6, 7, and 8 on Day 14 will be reduced and less ill patients will go home earlier, increasing the fraction of 1 and 2's on day 14.

Since the outcome is ordinal, a Wilcoxon rank sum test is used to control (no CSA) and CSA on day 14. The one-tailed null hypothesis is that the distribution of WHO scores is the same in two groups or worse in CSA, and the alternative is that the distribution of WHO scores in the CSA group is shifted lower. The effect size ($P_1 = \Pr(\text{Control} > \text{CSA})$) is the probability that a randomly selected observation from the control group has a score greater than one from CSA group. The null value for P_1 is 0.5 and the closer P_1 to 1, the bigger the effect.

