11.3 Stratification Factors

Randomization will be stratified by 1) age (<60 or ≥ 60 years), 2) WHO severity (4 vs. 5), and 3) presence or absence of comorbidities (at least one of the following- hypertension, coronary artery disease, congestive heart failure, or diabetes) with total of up to 8 strata and employ permuted block size of 3.

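### The primary Wilcoxon test ignores the three factors that randomisation is stratified on; it stays valid but becomes conservative and gives up some power if those factors are prognostic

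*Combined protocol and SAP*

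**What the plan says.** Section 11.1 gives the whole primary analysis in one sentence: a "Wilcoxon rank sum test will be used to compare the ordinal scale between groups on day 14". Section 11.2 powers that same test: 25 control and 50 CSA patients, one-sided 10% level, 81% power under Scenario 1 of Table 3. It also defines the effect size P1, which "is the probability that a randomly selected observation from the control group has a score greater than one from CSA group". Section 11.1 does not commit to reporting P1 or an interval for it.

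Section 11.3 states "Randomization will be stratified by 1) age (<60 or ≥ 60 years), 2) WHO severity (4 vs. 5") and adds comorbidity, giving up to 8 strata with permuted blocks of 3. Section 4.3 lists the same factors but a different age cut: randomisation "will be stratified by age (<60 or >60 years), WHO severity (4 vs. 5), presence or absence of comorbidities".

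The background treats all three factors as prognostic. Section 2.1 says "The case fatality rate increases with the severity of illness". Section 2.2 says "High-risk groups for severe COVID-19 have been identified as the elderly population"; it puts people with several chronic conditions, among them heart disease and diabetes, in the same category. The only model with baseline characteristics is the exploratory logistic regression of ventilator need in section 11.5.

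**The concern.** Stratified blocks force the two arms to be nearly balanced on the stratification factors. If those factors predict the day 14 score, chance differences between arms are smaller than under simple randomisation. The ordinary Wilcoxon variance does not know this: it still includes the spread in scores between strata. The test statistic is therefore divided by too large a standard error, and the test rejects too seldom under both the null and the alternative.

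The stake is efficiency, not validity. It matters most where the trial is weakest: Table 3 gives 62% and 48% power for Scenarios 2 and 3. The trial is open-label, so an adjusted primary analysis is credible only if it is fixed in advance.

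**Working it through.** **1. Reproducing the plan's figure.** Inputs are from section 11.2 and Table 3: N = 75, control fraction r = 1/3, one-sided α = 0.10 (z = 1.2816).

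- P1 for Scenario 1: Pr(Control > CSA) = 0.5466 and Pr(tie) = 0.2073. Counting ties as half, P1 = 0.5466 + 0.1037 = 0.650, the plan's 0.65. Without ties it is 0.547.
- Noether: power = Φ(√(12·r·(1−r)·N)·(P1 − 0.5) − z) = Φ(√200 × 0.1503 − 1.2816) = Φ(0.844) = 80.0%.
- With the tie correction, 200 is divided by 1 − Σp³ over the pooled category shares: 82.5%.
- Direct simulation of the Table 3 probabilities (20,000 trials): 83.1%.
- Noether gives 62.3% and 47.2% for Scenarios 2 and 3, against 62% and 48% stated.

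So the stated power is sound for the planned test.

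**2. Adding prognostic strata.** The documents give no odds ratios or stratum shares; those below are assumptions.

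- Design: N = 75, 8 strata, permuted blocks of 3 at 2:1, 10,000 trials per setting.
- Base shares: 30% WHO 5, 50% older, 60% comorbid.
- Model: logit Pr(Y ≤ k) = a(k, arm) − (β₁·WHO5 + β₂·older + β₃·comorbid), with each β a log odds ratio. The cut-points a are solved separately in each arm so that its overall distribution stays at its Table 3 column. P1 therefore stays at 0.650, 0.613 and 0.586 as prognosis varies.
- Tests at one-sided 0.10: tie-corrected Wilcoxon; and rank ANCOVA, which regresses midranks of the day 14 score on treatment and the three factors as main effects.

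Power is Wilcoxon → rank ANCOVA, in %.

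| Odds ratios (WHO/age/comorbidity) | Wilcoxon true error | Scenario 1 | Scenario 2 | Scenario 3 |
|---|---|---|---|---|
| none | 9.7 | 83.2 → 82.8 | 64.3 → 63.7 | 47.9 → 47.8 |
| 1.5 each | 9.5 | 82.9 → 83.4 | 64.9 → 65.4 | 48.8 → 49.3 |
| 3/2/1.5 | 9.0 | 84.2 → 85.8 | 64.9 → 67.8 | 50.0 → 52.8 |
| 5/3/2 | 7.4 | 86.0 → 89.4 | 65.8 → 71.8 | 48.5 → 54.9 |

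The Monte Carlo SE is at most 0.5 points for each power and 0.1 to 0.3 for the paired differences. Rank ANCOVA held its error at 9.5 to 10.2% in all settings. Moving the WHO 5 share between 15% and 50% shifts the largest gain to 2.8–3.9 points in Scenario 1 and 4.9–7.1 in Scenarios 2 and 3.

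**3. Different assumptions.** A second simulation used 8,000 trials per setting and shares of 25% WHO 5, 50% older and 65% comorbid. Odds ratios here are age/WHO/comorbidity. Wilcoxon error fell from 9.8% (no effects) to 8.7% (3/3/2) and 7.2% (4/5/2). Scenario 1 power, Wilcoxon against rank ANCOVA, was 82.3 vs 82.0, 84.2 vs 86.7 and 85.9 vs 89.4: the same pattern.

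**4. Choosing the adjusted test.**

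- A van Elteren test over all 8 strata has about 25/8 ≈ 3 controls per cell. With no prognostic effect it had 80.8% power against 82.3% for the plain Wilcoxon, a loss of 1.5 points.
- Stratified on WHO score alone, it is safer but recovers less. At 5/3/2 under the base shares its power is 87.6, 69.0 and 51.8% in Scenarios 1 to 3, and its error ranged from 8.5 to 9.8% across settings.
- A proportional-odds model does not fit the planning table. Scenario 1 cut-point odds ratios are 2.14, 4.00, 3.02, 2.79, 2.59, 2.44 and 2.36.

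**The case against.** The plan names a valid test and powers for that same test. In Scenario 1 the planned Wilcoxon exceeds the stated 81% in every row above, so nothing falls short of what is promised. The gain is about half a point at odds ratios of 1.5, and 1.6 points in Scenario 1 at 3/2/1.5. The largest figures need 5/3/2, a 30-fold difference in odds between extreme strata (5 × 3 × 2). The background statements concern fatality and the risk of severe disease in general, not the day 14 score among non-ICU patients scoring 4 or 5. Section 11.2 assumes everyone starts in category 4, in which case the strongest assumed factor contributes nothing. The error rates of 9.7% and 9.5% are within or close to simulation error of 10%. Finally, an adjusted test paired with an unadjusted interval for P1 could disagree near the boundary.

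Much of this stands. The loss is one of efficiency, its size is assumed, and only the stronger settings show clear conservatism. It does not remove the point. Score 5 is eligible under section 3.1 and is itself a stratum, and baseline WHO score is an earlier reading on the endpoint's own scale. Adjustment costs at most 0.6 points if the factors prove irrelevant. The interval can be labelled unadjusted and descriptive, with the decision resting on the adjusted test.

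**Conclusion.** The concern holds as an efficiency point. The planned test is valid, its type I error is not inflated, and 81% is not overstated for this reason. To the extent that the stratification factors are prognostic, the test is conservative and leaves power unused: about 0 to 3.4 points in Scenario 1 and about 0 to 6 in Scenarios 2 and 3, with the upper ends reached only under strong effects. With weak factors the loss is about half a point; with none it is zero. These sizes rest on the assumed odds ratios and stratum shares, and on main effects that are the same in both arms on the latent scale. The change is worth making because it uses data already collected before randomisation and has almost no downside.

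**What to change.** 1. Reconcile the age cut. Section 4.3 places a 60-year-old in no stratum and section 11.3 does not. State the cut that the randomisation system uses, and use the same one in the analysis.
2. In section 11.1, prespecify as the primary test a rank ANCOVA: midranks of the day 14 WHO score regressed on treatment, baseline WHO score (4/5), age group and comorbidity as main effects, with a one-sided test of treatment at 0.10. A van Elteren test stratified by baseline WHO score only is an acceptable, less efficient alternative; do not stratify on all 8 cells.
3. Report P1 with a confidence interval. Name the interval method, label the estimate unadjusted and descriptive, and state that ties count as half.
4. Keep the unstratified Wilcoxon as a sensitivity analysis, and use any proportional-odds model as supportive only.

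The cost is SAP wording: no extra patients, visits or measurements. The price if the factors turn out not to be prognostic is about 0.1 to 0.6 points of power.

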11.2 Sample Size /Justification

We expect to see higher grades of WHO COVID ordinal clinical scale in control group compared to the CSA treatment group, and propose to use a 1 to 2 randomization in favor of CSA group.

The total sample size of 75 evaluable participants will provide 81% power to reject the null hypothesis that the grade in control group is less than or equal to the CSA group with a 10% one-sided significance level when the true effect size, as measured by the probability that

Control grade is greater than CSA grade, is 0.65 or greater. Sample size and/or power for the various scenarios were calculated using nQuery 8 (StatSols Version 8.5.2.0).

The following provides the rationale for the alternate hypothesis effect size. We have assumed that all participants will be starting in category 4. Based on review of hospital data, about one third of such patients end-up in the ICU and about half of those patients will die. Of the two thirds that do not go to the ICU, most will be discharged in 2 weeks or less. We have therefore hypothesized that at 2 weeks following enrollment, the control group will be distributed as shown in the table 3.

We have hypothesized several scenarios to estimate the sample size needed to detect a CSA effect with reasonable power. We expect the effect of CSA will be to reduce ICU admissions, or to shorten time in the ICU and reduce deaths, so that the fraction in categories 6, 7, and 8 on Day 14 will be reduced and less ill patients will go home earlier, increasing the fraction of 1 and 2's on day 14.

Since the outcome is ordinal, a Wilcoxon rank sum test is used to control (no CSA) and CSA on day 14. The one-tailed null hypothesis is that the distribution of WHO scores is the same in two groups or worse in CSA, and the alternative is that the distribution of WHO scores in the CSA group is shifted lower. The effect size ($P_1 = \Pr(\text{Control} > \text{CSA})$) is the probability that a randomly selected observation from the control group has a score greater than one from CSA group. The null value for P_1 is 0.5 and the closer P_1 to 1, the bigger the effect.

A sample size of 25 in the control group and 50 in the CSA group will have 81% power to reject the null hypothesis (based on the 8 observable category probabilities for each group shown in table 3) in favor of the alternative hypothesis that an observation in the control group has a higher score on day 14 than an observation in the CSA group using a Wilcoxon (Mann-Whitney) rank-sum test with the type 1 error of 10% one-sided significance level.

Table 3. Scenarios and associated sample size and power.

		At Accrual	Control	CSA Scenario 1 ~50% benefit	CSA Scenario 2 ~40% benefit	CSA Scenario 3 ~30% benefit
8	Death	0	17%	8%	10%	12%
7	Hospitalized, vented, pressors	0	8%	4%	5%	5%
6	Hospitalized w invasive ventilation	0	8%	4%	5%	6%
5	Hospitalized non-invasive ventilation	0	5%	2%	3%	3%
4	Hospitalized on O2	100%	5%	2%	3%	3%
3	Hospitalized not on O2	0	10%	2%	4%	7%
2	Not hospitalized with symptoms	0	24%	39%	35%	32%
1	Not hospitalized with no symptoms	0	23%	39%	35%	32%
Effect Size (P1=Pr(Control>CSA)				0.65	0.61	0.59
Power & sample size ($\alpha=10\%$, 1-tailed)						
	Power with N=25 control, 50 CSA			81%	62%	48%
	Sample size for ~80% power; Ctl:CSA			25:50	45:90	75:150

11.3 Stratification Factors

Randomization will be stratified by 1) age (<60 or ≥ 60 years), 2) WHO severity (4 vs. 5), and 3) presence or absence of comorbidities (at least one of the following- hypertension, coronary artery disease, congestive heart failure, or diabetes) with total of up to 8 strata and employ permuted block size of 3.

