4.1 Patient Registration

To register a patient, the following documents will be completed by the research nurse or data manager and faxed and/or e-mailed to the Study Coordinator:

- Copy of required laboratory tests
- Signed patient consent form
- Eligibility Screening Worksheet

The research nurse or data manager at the participating site will then call and/or e-mail the Study Coordinator at each site to verify eligibility. To complete the registration process, each Coordinator will:

- assign a patient study number
- register the patient on the study
- randomize the patient to one arm or the other by entering data into OnCore
- fax or e-mail the patient study number and result of randomization to the participating site
- call the research nurse or data manager at the participating site and verbally confirm registration and randomization

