6. TREATMENT AND/OR IMAGING PLAN

6.1 Agent Administration

Treatment will be administered on an inpatient basis. Reported adverse events and potential risks are described in Section 10. Appropriate dose modifications are described in Section 7

Arm A Regimen Description					
Agent	Premedications; Precautions	Dose	Route	Schedule	Cycle Length
Neoral, Investigational, Generic Acceptable,	NA	2.5 mg/kg	PO	BID	7 days

N=50 Patients					

Arm B Regimen Description					
Agent	Premedications; Precautions	Dose	Route	Schedule	Cycle Length
None*, N= 25 Patients	NA	NA	NA	NA	7 days

*Note: The PI has undertaken thorough discussions with the sponsor and generation of placebo capsules is not feasible for the timing of this study.

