13.1 Study Oversight

This protocol is monitored at several levels, as described in this section. The Protocol Principal Investigator is responsible for monitoring the conduct and progress of the clinical trial, including the ongoing review of accrual, patient-specific clinical and laboratory data, and routine and serious adverse events; reporting of expedited adverse events; and accumulation of reported adverse events from other trials testing the same drug(s). The Protocol Principal Investigator and statistician have access to the data required for this at all times.

There are 2 sites in this protocol. The lead site is Baylor College of Medicine. The PI from Baylor College of Medicine ([name]) and the PI from the second site, Brigham and Women's

Hospital ([name]) will have a conference at least monthly to review enrollment, AEs, and administrative elements of this protocol.

All Study Investigators at participating sites who register/enroll patients on a given protocol are responsible for timely submission of data via the mechanism described elsewhere in this section. All studies are also reviewed in accordance with the enrolling institution's data safety monitoring plan.

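### A single printed block size of 3 in an open-label 2:1 trial lets anyone who sees all earlier allocations in a stratum know about 41 to 44% of assignments in advance; one-site staff can predict far fewer

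*Combined protocol and SAP*

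**What the plan says.** Section 11.3 lists three stratification factors (age, WHO score 4 or 5, comorbidity), "with total of up to 8 strata", and gives one block size: randomization will "employ permuted block size of 3". Site is not a factor.

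Section 4.3 sets the ratio at 2:1 and states: "Randomization will be open-label, using the permuted block method". It adds: "Randomization will be performed centrally at the Baylor College of Medicine by the Project Manager". Section 6.1 explains that "generation of placebo capsules is not feasible for the timing of this study", so each assignment is plain to the staff treating the patient.

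Section 4.1 describes the step differently. Each Coordinator is to "randomize the patient to one arm or the other by entering data into OnCore" and then pass the result to the participating site. Section 13.1 records that "There are 2 sites in this protocol", that the lead investigator and the statistician have continuous access to the data, and that the two site investigators confer at least monthly on enrolment.

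Nothing in the document varies the block size or withholds it from enrolling staff. Beyond central performance, no concealment of the sequence is described.

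**The concern.** With a 2:1 ratio, a block of 3 must contain two Neoral and one control. Once the control has appeared, the rest of the block is Neoral; after two Neoral, the next patient is control. A reader of the protocol knows the block size and the strata, and the trial is unmasked. The next slot can therefore sometimes be deduced from past assignments without access to the list. Central randomization protects the list but does not prevent this deduction.

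Someone who can foresee the next arm can time consent, or use the room left by the exclusions that section 3.2 calls only relative, so that patients with better prognosis fall into one arm. The primary analysis (section 11.1) is an unadjusted Wilcoxon rank-sum test, so it would not correct for such steering. Intention-to-treat analysis does not help either, because the selection happens before randomization.

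**Working it through.** **The plan's own figure.** The document gives no predictability figure. Its design figure is 81% power with 25 control and 50 CSA at 10% one-sided (section 11.2, Table 3, Scenario 1). From the Table 3 percentages, P1 = Pr(Control > CSA) + 0.5 × Pr(tie) = 0.547 + 0.103 = 0.650. Noether's formula gives power = Φ(√(12 × 1/3 × 2/3 × 75) × 0.150 − 1.2816) = Φ(14.142 × 0.150 − 1.2816) = Φ(0.840) = 80.0%. Simulation gives 80.8% without and 82.4% with tie correction. The 81% is reproduced. Block size does not enter this calculation.

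**Full visibility, complete blocks.** The inputs are block size 3 (section 11.3) and ratio 2:1 (section 4.3). N is Neoral and C is control; the three orders are equally likely.

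| Order | Slots certain in advance | Count |
|---|---|---|
| N N C | third | 1 |
| N C N | third | 1 |
| C N N | second and third | 2 |

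Share certain = (1 + 1 + 2) / 9 = 4/9 = 44.4%. By position it is (0 + 1/3 + 1) / 3, the same value. The best guess is right for (2/3 + 2/3 + 1) / 3 = 7/9 = 77.8% of patients, against 66.7% from always guessing Neoral.

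**Unfinished blocks.** With 75 patients spread over 8 strata, some blocks stay incomplete. Simulation gives a mean of 41% certain (95% range 35 to 48%), whether the strata are equal or uneven in size (both assumed).

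**An observer who sees one site only.** Each stratum's blocks interleave patients from both sites. An unseen patient at the other site may have closed the block, so this observer is never strictly certain. The prediction was computed with a Bayesian filter, with 9 patients per stratum and assumed site splits:

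| Share of patients at the other site | At least 90% predictable | Strictly certain |
|---|---|---|
| 10% | about 24% | 0% |
| 30% | about 9% | 0% |
| 50% | 0% | 0% |

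If the observer were told where blocks begin, strict certainty would be about 18% (50:50), 22% (70:30) or 33% (90:10). Nothing in the document gives one-site staff that information.

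**Illustration of error inflation, no drug effect.** Known Neoral slots receive patients with the day-14 distribution of the Table 3 Scenario 3 column. Known control slots receive patients like the control column. All other slots receive a mix of the two.

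| Visibility | Half of known slots used | All known slots used |
|---|---|---|
| Both sites | about 15% | about 20 to 21% |
| Same site only, 50:50, block boundaries granted | about 12% | about 13% (up to 14% in repeat runs) |

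**Mixed blocks of 3 and 6, sizes known, full visibility.** About 8% of allocations are strictly certain, but about 28% remain at least 90% predictable. The best guess is right for about 74 to 75%, down from 78%. If block boundaries were also known, about 30% would be certain, which is an upper bound.

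**The case against.** The strongest reply is that 44% describes the best-placed guesser. It needs complete blocks and sight of every earlier allocation in the stratum at both sites. Site is not a stratum, and no section sends one site's allocations to the other. At a 50:50 split, a one-site observer does no better than always guessing Neoral. The wider view is documented only for those who randomize centrally, the lead investigator and the statistician; the document does not show that they choose or time enrolment. This stands, and it limits the claim.

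The error figures are also fairly challenged. They borrow a hypothesised drug effect as the prognosis gap. Nothing in the document shows that staff could sort patients that well within strata already fixed on age, WHO score and comorbidity. They are illustrations only.

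Small blocks have a purpose too. With about 9 patients per stratum (75 / 8 = 9.4), they hold the 2:1 ratio closely. That is a reason to keep blocks short. It is not a reason to use one size or to print it.

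Central randomization and intention-to-treat analysis do not answer the point, because the prediction comes from past open assignments and acts before randomization.

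**Conclusion.** The point holds as a design weakness. One printed block size of 3, with visible 2:1 allocation, lets a person with full sight of both sites know about 41% of allocations in advance (44.4% in complete blocks). For staff at one site the share predictable with at least 90% confidence is about 0 to 24%, depending on the site split, which the document does not give.

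A reader might infer three stronger things that the document does not support:

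- That any enrolling clinician can foresee 44% of assignments. Blocks run across both sites, so this fails for one-site staff.
- That the 10% error rate is in fact inflated. The document shows an opportunity, not that anyone uses it. The figures of 15% and 20 to 21% require full visibility, deliberate steering and the assumed prognosis gap.
- That mixing block sizes alone solves the problem. The fall from 44% to 8% counts only strict certainty; near-certainty stays at about 28% while the sizes are known.

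The 4/9 is exact. The one-site and error figures are simulated under the stated assumptions and are less firm.

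**What to change.** In section 11.3, replace the fixed block size with centrally generated, randomly varying block sizes within strata, for example 3 and 6. Remove the sizes from the protocol and keep them in a restricted randomization document that enrolling staff cannot see. Both parts are needed. In the same edit, reconcile section 4.1 (each Coordinator randomizes) with section 4.3 (the Project Manager randomizes centrally), and state who may see allocations from both sites.

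The cost is one changed sentence on block size, a new randomization list and a short restricted document. The 2:1 balance becomes slightly looser in sparse strata: in simulation, the 95% range for the Neoral arm widens from 48 to 52 patients to about 47 to 53. The sample size of 75 and the stated 81% power are unchanged.
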